### **2.2 Study Design**

- 2.2.1 Single site, non-randomized, prospective, phase IV trial
- 2.2.2 Study group will include organ confined prostate cancer
- 2.2.3 Data collected will include patient demographics, pathology data, tumor stage, SBRT dose fractionation scheme, dose received by adjacent critical normal tissues, tumor recurrence data, and acute and late toxicities.
- 2.2.4 Follow up data will be collected during the patient's standard office visits. The anticipated duration of this study is 5 years

### **2.3 End Points**

- 2.3.1 Primary endpoints will be biochemical control rate
  - Serial blood tests for prostate specific antigen (PSA) levels will be obtained at regular intervals
  - The "Phoenix definition" for biochemical recurrence (nadir + 2 ng/ml) will be used
- 2.3.2 Secondary endpoint will be late toxicity rate.
  - Grading of acute and late complications is defined in Section 12.3 (Appendix III)

## **3.0 Patient Selection**

### **3.1 Eligibility Criteria**

- 3.1.1 Patient age of at least 18 years
- 3.1.2 Zubrod performance status of 0-3
- 3.1.3 T1-3N0M0 adenocarcinoma of the prostate
- 3.1.4 Prostate volume  $\leq$  100 cc
- 3.1.5 No prior pelvic radiotherapy except as part of combination therapy for prostate cancer
- 3.1.6 Signed study-specific consent form

### **3.2 Exclusion Criteria**

- 3.2.1 Extension of local tumor to involve adjacent organs other than seminal vesicles (T4)
- 3.2.2 Prostate volume  $>$  100 cc
- 3.2.3 Nodal involvement
- 3.2.4 Metastatic disease
- 3.2.5 Prior central pelvis radiotherapy except as part of combination therapy for prostate cancer
- 3.2.6 History of scleroderma
- 3.2.7 Patients with psychiatric or addictive disorder that would preclude obtaining informed consent

#### **4.0 Pretreatment Evaluation**

- 4.1 Patient history, including prior radiation and chemotherapy treatments
- 4.2 Physical examination including digital rectal examination
- 4.3 Tissue biopsy confirming a diagnosis of malignancy
- 4.4 Abdominopelvic CT scan or MRI as clinically indicated
- 4.5 Bone scan and chest x-ray as clinically indicated
- 4.6 CBC, platelets, bilirubin, albumin, AST, ALT, PT, PTT as clinically indicated

#### **5.0 Fiducial Placement**

- 5.1 Three gold fiducials will be placed within the prostate gland under ultrasound guidance in different locations
- 5.2 Fiducials should be placed at least 7 days prior to simulation because of the possibility of migration

#### **6.0 Simulation**

- 6.1 Bowel Prep on the morning of simulation including Dulcolax® laxative and a Fleet Enema.
- 6.2 Balloon catheter with 60 cc diluted barium contrast positioned in the rectum to stabilize pelvic anatomy
- 6.3 Custom body immobilization with the BodyFix system
- 6.4 CT simulation without IV contrast with 1-2 mm slice thickness, including at least 5 cm above and below the treatment volume.
- 6.5 3-point leveling tattoos
- 6.6 Contrast enhanced MRI of the pelvis with 1-3 mm slice thickness (saline-filled 60 cc rectal balloon in place); CT-MRI fusion for target volume and normal tissue delineation

#### **7.0 Radiation Treatment Planning**

##### **7.1 Target Definition**

- 7.1.1 Gross tumor volume (GTV) is contoured on the planning CT scan. MRI images will be registered to the planning CT dataset to assist in constructing the GTV and normal structure volumes. GTV will include the entire prostate gland. The proximal seminal vesicles may be included in the GTV at the discretion of the treating radiation oncologist based on high risk features (e.g. Gleason score > 6 and PSA > 15 ng/ml). GTVMR may be contoured to delineate the visible MR abnormality and may be targeted for an integrated boost at the discretion of the treating physician.
- 7.1.2 Clinical target volume (CTV) will be equal to the GTV
- 7.1.3 Planning target volume (PTV) will be defined as the CTV plus a 3-5 mm expansion margin throughout except posteriorly by the rectum where a 2-3 mm margin will be used. For high risk patients with organ confined disease (e.g. Gleason score 8-10 and/or PSA > 20 ng/ml), the PTV will also include a 5-8 mm margin on the involved side of the prostate.

##### **7.2 Dose-Specification**

- 7.2.1 The total prescription dose for SBRT will be 30 – 40 Gy in 4 – 5 fractions delivered 2 to 3 times per week. The total prescription dose for SBRT as a boost after prior conventionally fractionated external beam pelvic radiotherapy (45 Gy in 25 fractions) will be 19 – 21 Gy in 2 – 3 fractions delivered 2 to 3 times per week. At the discretion of the treating radiation oncologist, an integrated boost of ~ 1 Gy per fraction may be directed at the MR abnormality.

- 7.2.2 Radiation beams will conform to the PTV outline without additional margin and the dose will be prescribed to the isodose line (IDL) that covers at least 95% of the PTV. The 105% IDL should be confined to the PTV.
- 7.2.3 Conformality index (CI) = Prescription IDL volume / PTV volume  
Goal =  $CI \leq 1.2$
- 7.2.4 Gradient index (GI) = 50% Prescription IDL volume / Prescription IDL volume  
Goal =  $GI \leq 3$

### **7.3 Normal Tissue Dose Constraints**

- 7.3.1 The normal structures that will be contoured using the planning CT/MR fusion are listed below with their respective dose constraints (five fractions) as derived from the available literature:

STRUCTURE	VOLUME	DOSE
Spinal Cord	D max	22.5 Gy
	< 10 cc	20 Gy
Cauda Equina	D max	27.5 Gy
	< 10 cc	25 Gy
Sacral Plexus	D max	30 Gy
	< 10 cc	27.5 Gy
Anterior Rectal Wall	D max	No more than 105% Rx
Posterior Rectal Wall	D max	20 Gy
Lateral Rectal Wall	D max	No more than 100% Rx
	< 3 cc cumulative (both sides)	50 Gy
Rectum superior to prostate	D max	30 Gy
	< 10 cc	25 Gy
Small Intestine	D max	30 Gy
	< 10 cc	25 Gy
Prostatic Urethra	D max	No more than 105% Rx
Bladder	D max	No more than 105% Rx
	< 10 cc	20 Gy
Penile Bulb	D max	No more than 105% Rx
	< 3 cc	30 Gy
Femoral Heads	< 10 cc cumulative (both sides)	30 Gy
Skin not within fold	D max	25 Gy
Skin within fold (e.g. gluteal fold)	D max	20 Gy

## **8.0 Stereotactic Body Radiotherapy Treatment Delivery**

### **8.1 Premedication**

The decision to premedicate a patient prior to prostate SBRT is at the discretion of the treating radiation oncologist. While there is no universal agreement, the following are a list of agents that have been suggested by some investigators to potentially reduce patient discomfort and possibly prevent acute and/or late toxicity if used as premedication prior to prostatic SBRT.

- 8.1.1 Corticosteroids (Decadron 4-10 mg PO or equivalent) 15-60 minutes prior to each fraction for the intended purpose of modulating immediate inflammatory effects.
- 8.1.2 Analgesic medication for patient comfort during long treatment duration.
- 8.1.3 Anti-anxiety medication for patient comfort during long treatment duration.
- 8.1.4 Tamsulosin (Flomax) starting on the first day of treatment and continuing for at least 3 months
- 8.1.5 Bowel Prep on the morning of each treatment, including Dulcolax® laxative formula and a Fleet Enema. The patient may also be asked to start a bowel regimen 3 days

prior to the simulation with Milk of Magnesia and Gas-X and continue throughout the course of treatment.

- 8.1.6 Amifostine 1500 mg mixed in saline and instilled into the rectum 20 minutes prior to each treatment

**8.2 Treatment**

- 8.2.1 The medical physics staff will perform routine quality assurance checks on the treatment machine to ensure that the mechanical isocenter stability is within specification (ie. diameter  $\leq$  1.5 mm).
- 8.2.2 The medical physics staff will perform patient-specific quality assurance measurements to ensure that the treatment plan is deliverable and that the dose distribution is accurate.
- 8.2.3 The patient will be positioned in the custom immobilization device on the Hexapod® treatment couch and the rectal balloon will be inserted and filled with 60 cc of barium contrast. He will then be aligned to 3-point setup points with the in-room lasers.
- 8.2.4 Daily CT localization of the GTV isocenter is required prior to each fraction. Once the patient is properly positioned, a cone-beam CT of the treatment area will be acquired, fused, and aligned to the treatment planning CT utilizing the patient’s internal anatomy, fiducial markers, and contrast-filled rectal balloon. Translational and rotational adjustments of patient positioning are performed as indicated. If adjustments are required, an orthogonal (ex. AP and LATERAL) set of electron portal images or a second cone-beam CT is then obtained prior to treatment to confirm proper alignment of the isocenter.
- 8.2.5 Either multiple coplanar or noncoplanar static gantry angle intensity-modulated fields or rotational arcs will be utilized.
- 8.2.6 Only photon (x-ray) beams will be used, preferably in energies of 6-18 MV.

**9.0 Drug Therapy**

- 9.1 The use of hormone therapy is left to the discretion of the treating radiation oncologist and the patient’s urologist.
- 9.2 All forms of androgen suppression including neoadjuvant, concurrent, and adjuvant hormone therapy may be recommended.
- 9.3 Chemotherapy is rarely if ever used for localized prostate cancer but is left to the discretion of the medical oncologist. Chemotherapy is not allowed during SBRT. Ideally, chemotherapy should not have been given within 30 days of starting radiation and should not resume until at least 2 weeks after completing radiation. In addition, it is not recommended to perform SBRT when targeted anti-angiogenesis therapy is planned within 2 months of the procedure.

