### **Hormone Therapy**

Hormone therapy may be given at the discretion of the patient's urologist and/or radiation oncologist based on high risk features. All forms of androgen suppression including neoadjuvant, concurrent, and adjuvant hormone therapy may be recommended.

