**10.0 Patient Assessment**

**10.1 Study Parameters**

The following are suggested patient follow-up intervals and evaluations that may be performed to either assess for treatment toxicity or tumor response to SBRT:

Assessment	Pre-Rx	Post-Rx 6 wk	Post-Rx 3 mo	Post-Rx 6 mo	Post-Rx 9 mo	Post-Rx 1 yr
H&P / Weight	X	X	X	X	X	X b
Disease status	X	X	X	X	X	X b
AUA/EPIC Questionnaire	X	X	X	X	X	X
Toxicity Assessment		X	X	X	X	X b
PSA	X	X	X	X	X	X

AST/ ALT / Alk Phos	X a					
Total Bilirubin	X a					
PT/ PTT	X a					
Creatinine	X a					
CBC with Platelets	X					
Bone scan	X a					
CT/MR abdomen/pelvis	X					X b

- a. if clinically appropriate  
b. at the discretion of the treating radiation oncologist

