## **10.3 Toxicity**

**10.3.1** The patient will fill out the American Urological Association (AUA) Symptom Score Sheet and Expanded Prostate Cancer Index Composite (EPIC) questionnaire for gastrointestinal, urinary and sexual quality of life. (14) (Appendix IV and Appendix V, respectively)

**10.3.2** The investigator will report and record all serious adverse events that occur. Adverse events should be reported using the CTC grading system (Appendix III).

**10.3.2** Examples of anticipated acute adverse events include:

- General malaise
- Urinary irritative or obstructive symptoms – dysuria, increased urinary frequency, nocturia, weak stream, hesitancy, and possible urinary retention
- Rectal irritation – loose stools, cramping, straining, hemorrhoidal inflammation
- Radiation dermatitis – dryness, tanning, redness, itching
- Localized hair loss
- Musculoskeletal pain

**10.3.3** Examples of anticipated late adverse events include:

- Bleeding, ulceration and/or perforation of the bladder, rectum, or small bowel
- Neurologic changes including motor weakness, numbness, paresthesias, and/or bowel or bladder dysfunction
- Persistent changes in bowel or bladder habits
- Small bowel obstruction
- Urethral stricture resulting in urinary retention
- Localized skin fibrosis, edema, and/or ulceration
- Erectile dysfunction
- Radiation-induced secondary malignancy

**10.3.4** Reporting of unanticipated or serious adverse events will be reported according to the institutions IRB policy. An unanticipated adverse event is defined as follows:

Any serious adverse effect on health or safety or any life-threatening problem or death caused by, or associated with, stereotactic body radiotherapy, if that effect, problem, or death was not previously identified in nature, severity, or degree of incidence in the investigational plan or application (including a supplementary plan or application), or

any other unanticipated serious problem associated with a treatment that relates to the rights, safety, or welfare of subjects.

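### A pooled late sexual-toxicity rate cannot be attributed to SBRT alone, because discretionary hormone therapy is not separated in the analysis

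*Combined protocol and SAP*

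**What the plan says.** **Hormone therapy.** Section 9.1: "The use of hormone therapy is left to the discretion of the treating radiation oncologist", shared with the patient's urologist. Section 9.2: "All forms of androgen suppression including neoadjuvant, concurrent, and adjuvant hormone therapy may be recommended". The Hormone Therapy paragraph of the schema gives the same discretion but ties it to risk ("radiation oncologist based on high risk features"). Section 9 does not repeat that condition.

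**Sexual toxicity.** Section 10.3.3, under "Examples of anticipated late adverse events include", lists "Erectile dysfunction". Section 11.1.2 names it among the late effects of SBRT. The follow-up form (Appendix VIII, item 4) has an impotence row in its late block, under a heading for events related to radiation.

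**Endpoint and analysis.** Section 2.3.2: "Secondary endpoint will be late toxicity rate". It adds: "Grading of acute and late complications is defined in Section 12.3 (Appendix III"). Appendix III, which is numbered 13.3, has no row for erectile dysfunction or any other sexual toxicity. Section 11.5 plans overall survival, biochemical control and the incidence of serious adverse events. It does not mention late toxicity, EPIC or hormone exposure.

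**Data.** The row "AUA/EPIC Questionnaire" in 10.1 is marked before treatment, at 6 weeks, at 3, 6 and 9 months, and at 1 year, as a suggested schedule. Follow-up form item 6 records systemic agents with start and stop dates. Item 10 records hormone therapy given for recurrence.

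**The concern.** That androgen suppression impairs sexual function is general clinical knowledge, not a statement in the documents. If it is accepted, a man on hormones can be impotent at a late visit because of the drug, the radiation or both. The design is single-site and non-randomized with no control arm, so no comparator can absorb the drug's part.

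Hormones may be neoadjuvant, concurrent or adjuvant, so exposure can start before the Pre-Rx EPIC or overlap later visits. A baseline taken on hormones is already lowered and can hide a later decline. Hormones started after baseline can produce a decline that SBRT did not cause.

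Late toxicity is the only secondary endpoint and bears on the claim of acceptable complication rates in 2.1.1. The Introduction also reads sexual outcome across modalities: it cites a 32-patient EPIC series with falls of 45%, 49% and 25% in the sexual summary, function and bother scores, and the conclusion that erectile dysfunction was comparable with other radiotherapy. A pooled rate from a T1-3 cohort with an unknown share of men on hormones could not support a reading of that kind.

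**Working it through.** **No plan figure to reproduce.** The documents state no sample size, expected erectile dysfunction rate or expected hormone share. Every rate below is an assumption, used only to show the range.

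**1. Pooled impotence rate.** Let *h* be the share of men on hormones, *r1* the late rate with hormones and *r0* the rate without.

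- Pooled rate = *h*·*r1* + (1 − *h*)·*r0*
- Excess over the no-hormone rate = *h*·(*r1* − *r0*)

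With *r0* = 0.40 and *r1* = 0.70:

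| *h* | Pooled rate | Excess | Excess as share of pooled |
|---|---|---|---|
| 0.1 | 0.07 + 0.36 = 0.43 | 0.03 | 0.03/0.43 = 7% |
| 0.3 | 0.21 + 0.28 = 0.49 | 0.09 | 0.09/0.49 = 18% |
| 0.5 | 0.35 + 0.20 = 0.55 | 0.15 | 0.15/0.55 = 27% |

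The wider grid is *r0* from 0.2 to 0.5, *r1* from 0.5 to 0.9 (with *r1* > *r0*) and *h* from 0.1 to 0.5:

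- Smallest excess: 0.1 × (0.5 − 0.4) = 0.01, about 2% of a pooled 0.41.
- Largest excess: 0.5 × (0.9 − 0.2) = 0.35, about 64% of a pooled 0.55.
- The excess is 0 if *h* = 0 or *r1* = *r0*.

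This assumes that every impotent man is ticked. The form asks for radiation-related events, so an investigator may leave the box empty for a man on hormones. That would pull the rate the other way.

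**2. Change in EPIC sexual score, if it is analysed.** Suppose hormones lower the score by *d* while they act. Let *p* be the share of men affected at the Pre-Rx questionnaire but no longer at the later visit, and *q* the share affected only at the later visit. A man affected at both contributes about zero. The error in the mean decline is *q*·*d* − *p*·*d* = (*q* − *p*)·*d*. It overstates the decline if *q* > *p* and understates it if *q* < *p*. The documents give neither share, so the sign is unknown.

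**3. Can exposure be separated with the planned data?** Largely yes. Item 6 has agents and dates, and item 10 identifies hormones for recurrence. There are gaps: the data list in 2.2.3 does not name hormone therapy, the treatment form (Appendix VII) has no field for it, and item 6 sits on a follow-up form, so it is unclear whether use before SBRT is entered. The patient demographic form (Appendix VI) is in the index but not in the text I had, so it may cover this.

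**The case against.** The strongest objection is that no planned analysis exists to be biased. Appendix III cannot grade erectile dysfunction, 11.5.2 counts only serious adverse events, EPIC is in no endpoint, and its schedule is only suggested. On this view the real gap is that late toxicity has no components, grade threshold, time point or analysis. That stands as far as it goes: whether impotence enters the late toxicity rate is not settled. But the protocol labels it a late radiation toxicity in three places and collects it on the form, so the natural reading of 2.3.2 includes it. The missing grading is a reason to specify its handling.

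A reader might infer that hormone therapy is unrestricted. Section 9 alone reads that way, but the schema ties it to high risk features. The two passages must be reconciled. The schema condition also means that hormone use would follow risk group and probably pelvic radiotherapy, so users and non-users would differ in more than the drug.

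A reader might extend the point to fatigue. The follow-up form lists fatigue as an acute event, so it does not bear on the late endpoint.

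It is also fair to say that the form's heading asks for attribution and that item 6 holds the needed dates. What is missing is mainly the pre-specified split. Finally, no section commits the trial to a formal comparison with the cited series. The harm is to interpretation, not to a planned test.

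**Conclusion.** The concern holds in a limited form. With discretionary hormones, no control arm and no separation by exposure, a pooled late sexual-toxicity rate cannot be attributed to SBRT alone. A reader might go further and infer that the sexual part of late toxicity is not an SBRT effect. The documents do not support that: men without hormones still contribute, and the pooled rate is a mixture that includes whatever SBRT does.

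The size is undetermined. The range of 1 to 35 points rests wholly on assumed rates, and on the clinical premise that hormones impair sexual function. The net direction is also unknown, because of baseline timing and possible attribution at the tick box. The point affects interpretation of the secondary endpoint.

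**What to change.** In 2.3.2 and 11.5.2:

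- Report late impotence and the EPIC sexual domain separately for men with no hormone therapy planned or started as part of initial treatment, and for men with it. A split into never and any use would classify men by later events, including hormones given for recurrence.
- Base statements about SBRT on the no-hormone group.
- Using item 6 dates, flag visits on drug. Exclude or flag visits after hormones begin for recurrence (item 10).
- Do not use a Pre-Rx EPIC completed after hormones began as the baseline for sexual change.
- Tabulate risk group and pelvic radiotherapy beside each group, and do not read the difference between groups causally.
- State how impotence is graded, since Appendix III has no row for it.

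Confirm that hormone use before SBRT is entered in item 6, and add hormone therapy to the list in 2.2.3. Reconcile the schema's Hormone Therapy paragraph with section 9.

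The cost is a few sentences, one table split, a grading rule and a check of the form. Treatment does not change. The main downside is that the SBRT-only sexual result comes from fewer, mostly lower-risk men and may not carry over to high-risk patients.

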### **2.1 Hypothesis**

- 2.1.1 For selected patients with localized prostate cancer (clinical stage T1-2N0M0), stereotactic body radiotherapy (SBRT) is technically feasible with acceptable complication rates.
- 2.1.2 Biochemical control with stereotactic body radiotherapy (SBRT) will be at least as good as standard fractionation radiation therapy

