## **10.2 Response Evaluation**

### **10.2.1 Prostate Specific Antigen (PSA)**

- Will be obtained every 3 months for the first 2 years, then as indicated at the discretion of the treating physician.
- Biochemical failure defined as nadir + 2 ng/ml
- Repeat imaging including abdominopelvic CT scan, MRI, or bone scan as clinically indicated.

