### **11.5 Statistical Analysis**

**11.5.1** The overall survival and biochemical control rates will be analyzed.

**11.5.2** The incidence rate for any serious adverse events will be calculated.

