**13.8 Appendix VIII**

**FOLLOW-UP VISIT FORM – Page 1 of 2**

1. Name \_\_\_\_\_ (last) \_\_\_\_\_ (first)

2. RT Number \_\_\_\_\_

3. Date of Visit: \_\_\_\_ / \_\_\_\_ / \_\_\_\_\_

4. Blood work:

Lab		Date:	Date:	Date:
Total Bilirubin				
Albumin				
Alkaline Phosphatase				
ALT	AST			
PT	PTT			
Creatinine				

4. Radiation Therapy related adverse events

Adverse Event	CTC V3.0 Grade	Timing	Treatment	Comments
ACUTE				
 Fatigue				
 Weight loss				
 Diarrhea				
 Urinary frequency/urgency				
 Dysuria				
 Alopecia				
 Radiation dermatitis				
 Musculoskeletal Pain				
 Neuropathy, Motor				
 Neuropathy, Sensory				
LATE				
 GI Bleeding				
 GI Ulceration				
 GI Perforation				
 GI Stricture				
 Fistula				
 GU Bleeding				
 GU Ulceration				
 GU Perforation				

 GU Stricture				
 Sterility				
 Impotence				
 Pelvic bone injury				
 Neuropathy, Motor				
 Neuropathy, Sensory				

5. Serious adverse event?  No  Yes, submit report to HIC

6. Has systemic therapy been given?  No  Yes

If yes, list therapy

Agent(s)	Start Date	Stop Date
_____	____/____/____	____/____/____
_____	____/____/____	____/____/____
_____	____/____/____	____/____/____

7. PSA since last follow-up visit  No  Yes, date \_\_\_\_/\_\_\_\_/\_\_\_\_

Current Level \_\_\_\_\_ ng/ml

Nadir Level \_\_\_\_\_ ng/ml

8. Radiologic Imaging since last follow-up visit  No  Yes, date \_\_\_\_/\_\_\_\_/\_\_\_\_

CT Scan Date \_\_\_\_/\_\_\_\_/\_\_\_\_

Bone Scan Date \_\_\_\_/\_\_\_\_/\_\_\_\_

9. Disease Status

No evidence of tumor

Biochemical recurrence

Date \_\_\_\_/\_\_\_\_/\_\_\_\_

Local recurrence within the treatment volume

Date \_\_\_\_/\_\_\_\_/\_\_\_\_

Distant recurrence, specify site \_\_\_\_\_

Date \_\_\_\_/\_\_\_\_/\_\_\_\_

10. Additional treatment for recurrent disease

Surgery

Yes  No

Date of surgery \_\_\_\_/\_\_\_\_/\_\_\_\_

Hormone therapy, agents \_\_\_\_\_

Yes  No

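### Discretionary androgen suppression acts on the PSA that defines the primary endpoint, and the plan has no rule separating it from SBRT, so the overall control rate cannot on its own support hypothesis 2.1.2

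*Combined protocol and SAP*

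**What the plan says.** Section 2.3.1 sets the endpoint: "Primary endpoints will be biochemical control rate". It adds that the Phoenix definition "for biochemical recurrence (nadir + 2 ng/ml) will be used", and section 10.2.1 repeats that definition. Neither section says which PSA values may supply the nadir, or how to treat values taken during or after androgen suppression.

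Section 9.1 leaves hormone therapy to the treating radiation oncologist and the urologist. Section 9.2 adds: "All forms of androgen suppression including neoadjuvant, concurrent, and adjuvant hormone therapy may be recommended". The Schema makes high-risk features the basis for use. No duration is stated, and no criterion in sections 3.1 or 3.2 limits it.

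On PSA timing, section 10.2.1 states: "Will be obtained every 3 months for the first 2 years, then as indicated at the discretion of the treating physician". The whole analysis of the primary endpoint is section 11.5.1: "The overall survival and biochemical control rates will be analyzed". That rate has to bear on hypothesis 2.1.2: "Biochemical control with stereotactic body radiotherapy (SBRT) will be at least as good as standard fractionation radiation therapy".

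The follow-up form (Appendix VIII) asks at item 6, "Has systemic therapy been given", with agents and start and stop dates. Item 10 separately records hormone therapy given for recurrent disease.

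**The concern.** Androgen suppression lowers PSA whether or not radiation has controlled the tumour, and PSA is the only measurement behind the endpoint. A man on suppression may show no nadir + 2 rise even if his disease is not controlled. Once suppression stops, his PSA is compared with a nadir that the drug produced. The men chosen for suppression are those with high-risk features, who are also the men most likely to fail, so use and prognosis are linked. The design is single-site and non-randomised (section 2.2.1), and nothing in it balances hormone use.

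At stake is what the headline rate means. Hypothesis 2.1.2 is about control with SBRT. A single rate over all men would depend partly on how often, and for how long, suppression was prescribed locally.

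**Working it through.** The plan gives no sample size, reference rate, margin or time point, so it has no figure of its own to reproduce. The check has two parts.

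**1. What the rule does when applied as written**

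- *During suppression.* Failure requires PSA ≥ nadir + 2. With PSA held down by the drug, the rule tends to return no failure, and the man counts as controlled. The bias is upward.
- *After suppression ends.* Let N_on be the lowest PSA on the drug and N_off the lowest PSA after it. If N_on < N_off, the threshold N_on + 2 is lower than N_off + 2, so recovery of PSA alone can bring a man closer to a recorded failure. The bias may be downward.
- *Timing.* The fixed 3-monthly schedule covers 2 years. Neoadjuvant, concurrent and adjuvant use all bear on that period.
- *Is a mixed cohort realistic?* In the series of 38 patients cited in the Introduction, 18 had SBRT as a boost after external beam radiotherapy and androgen deprivation (18/38 = 47%), and freedom from recurrence was reported for all patients together.

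**2. An illustration of size**

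Input from the documents: 3-year biochemical control of 77.7% in high-risk men, from the 73-patient boost series in the Introduction.

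Assumptions not in the documents:
- constant hazard;
- the 77.7% is free of hormone effect;
- suppression runs through 24 months after SBRT and hides every failure in that time;
- 30-50% of the high-risk group is so treated.

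Steps:
- Hazard: h = −ln(0.777)/3 = 0.0841 per year.
- True 2-year control: exp(−2h) = exp(−0.168) = 0.845, or 84.5%.
- Recorded 2-year control in men suppressed throughout: 100%, which is 15.5 points too high.
- A high-risk group with share f suppressed reads 84.5 + 15.5f. For f = 0.30 this is 84.5 + 4.65, about 89.2%. For f = 0.50 it is 84.5 + 7.75, about 92.3%. The excess is about 5 to 8 points.

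Twenty-four months is the extreme case at this time point. If suppression were shorter and PSA had recovered before 2 years, the hidden failures would already have surfaced, and masking alone would leave the 2-year rate near 84.5%.

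**The case against.** The strongest reply is that the plan is silent and nowhere says that hormone therapy will be ignored. Item 6 of the follow-up form already collects agents and dates, so an analyst could separate the groups. On this view the point is one consequence of a one-sentence analysis section. That stands in part. The gap lies mainly in the endpoint and analysis rules, and the documents do not show an intention to pool. But 11.5.1 is the whole analysis text, so any separation would be chosen after the data are seen.

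The inputs are also weak. The boost series had 7 high-risk failures, nothing shows it was free of hormone effect, and the share and duration are assumed. This stands, and the figures above serve only as illustration.

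A reader might go further in three ways that the documents do not support:

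- *The 3-year rate must also be inflated.* Removing the suppressed years from the hazard assumes that failures are prevented or postponed. If they are only hidden, they surface once suppression ends and PSA recovers, and the 3-year rate returns towards 77.7%.
- *A rate in men without hormone therapy would be the effect of SBRT.* It would not. The trial is non-randomised, and 45 Gy of pelvic radiotherapy is also discretionary.
- *Baseline hormone therapy is not recorded.* This cannot be established. The index lists a Patient Demographic Form (Appendix VI) that is not in the available text.

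**Conclusion.** The concern holds as a should-fix point and is cheap to mend. Under the stated endpoint rule and the hormone use allowed, the overall biochemical control rate mixes drug and radiotherapy and cannot by itself support hypothesis 2.1.2. The expected bias is upward while men are on suppression and possibly downward after withdrawal, so the net direction depends on when the rate is read.

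The size cannot be determined from the documents. The 5 to 8 points at 2 years rest on full masking for 24 months, a constant hazard taken from one small series assumed free of hormone effect, and an assumed share of 30-50%. No inflation at 3 years is claimed. The conclusion does not depend on these numbers. It follows from applying the nadir + 2 rule to men whose PSA is being suppressed.

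**What to change.** In 2.3.1 and 11.5.1, state the following:

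- Biochemical control will be reported overall and separately by whether androgen suppression was planned as part of initial treatment, as recorded before SBRT. The group with none planned is the main evidence for hypothesis 2.1.2. Grouping on the plan avoids defining groups by later events.
- Hormone therapy given for recurrence (follow-up form, item 10) does not move a man out of his group, and the recurrence counts as a failure. Without this, men would be dropped because they failed.
- Hormone therapy started before a PSA failure and outside the initial plan is handled by a stated rule, with a sensitivity analysis counting it as failure.
- In the planned-suppression group, the time origin stays at SBRT and any failure during suppression counts. A sensitivity analysis takes the nadir from PSA values after the recorded stop date (item 6) and shows time on suppression separately.

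Record planned hormone therapy at baseline if no existing form does so.

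The cost is wording in two sections and perhaps one form item, with no added visits or tests. Who receives hormone therapy is unchanged. The drawback is that the estimate in men with none planned rests on fewer, lower-risk men. It will be less precise, and it remains a non-randomised rate.
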